8.3 Clinical Safety Assessments

Details regarding the DMC, DEC, and SC are provided in Appendix 1.

AEs will be reported and followed by the investigator as specified in Section 8.4 and Appendix 3.

Any clinically relevant changes occurring during the trial must be documented. Any clinically significant abnormalities persisting at the end of the trial/early withdrawal will be followed up by the investigator until resolution or until a clinically stable condition is reached depending on if they correspond to an AE, AESI or an SAE as per Section 8.4.6.

The trial will include the following evaluations of safety and tolerability according to the time points provided in the Schedule of Activities, Section 1.3.

8.3.1 *Physical Examination*

A complete (full) physical exam should be performed during screening period. At subsequent visits, a symptom-directed/clinically indicated (brief) physical examination may be performed.

Full Physical Examination:

The investigator or qualified designee will perform a full physical examination according to standard of care at the time points specified in the Schedule of Activities, Section 1.3. After the first dose of trial treatment, new or worsening findings that are considered clinically significant should be reported as AEs.

Genmab

Brief Physical Examination:

For cycles that do not require a full physical examination (as specified in the Schedule of Activities, Section 1.3), the investigator or qualified designee will perform a symptom-directed physical examination as clinically indicated prior to trial treatment administration. After the first dose of trial treatment, new or worsening findings since the last assessment that are considered clinically significant should be documented as AEs.

8.3.2 Body Measurements

8.3.2.1 Height

Height (without shoes) must be measured at screening and rounded to the nearest centimeter or inch.

8.3.2.2 Weight

Body weight (without overcoat and shoes) will be measured as indicated in the Schedule of Activities (Section 1.3) and rounded to the nearest kilogram or pound.

8.3.3 Vital Signs

Vital signs, including temperature (°C or °F), blood pressure (mm Hg), and heart rate (beats/min) should be measured with the subject in a supine or reclined position and recorded. Subjects should be resting and in a horizontal or half laid position for at least 10 minutes before vital signs are measured. Temperature should be measured as an oral, axillary, rectal, or ear temperature. The temperature should be documented as a value corrected according to local standards.

Within each visit, preferably the same equipment shall be used for vital sign measurements.

Vital signs will be measured as indicated in the Schedule of Activities (Section 1.3) according to Table 1-4, Table 1-8, Table 1-12, and Table 1-19.

On infusion days, vital signs should be assessed as described in Table 1-4 and Table 1-12 for GEN1053 monotherapy and in Table 1-8 and Table 1-19 for GEN1053+IM combination therapy, respectively.

8.3.4 Electrocardiograms

The ECGs will be recorded digitally at the sites by using the standard 12-leads as indicated in the Schedule of Activities (Section 1.3).

For the ECG recordings, the subject must be resting and in a supine or reclined position for at least 10 minutes. Any irregularity observed or occurring during the ECGs (eg, vomiting, cough) should either induce a repeat of the ECG or be annotated with the description and time of the occurrence.

ECGs will be performed in accordance with the ECG manual issued by the vendor. Digital ECGs will be transmitted from the sites electronically to a central laboratory for a treatment-blinded measurement of the cardiac intervals and morphologic assessment by a central cardiologist.

The QTc will be calculated using Fridericia's formula:

$$QTc_F = rac{QT}{\sqrt[3]{rac{RR}{(1s)}}}$$

An overall interpretation of the ECGs will be performed by the investigator, or the investigator may delegate this task to a cardiologist, if applicable. The investigator should interpret the ECG using the paper ECG reading from the ECG machine, and sign and date the printout. In case of discrepancy between central and the investigator ECG readings, the central reading will be used for trial analysis purposes.

8.3.5 ECOG Performance Status

The ECOG PS will be assessed by the investigator as indicated in the Schedule of Activities, Section 1.3. PS will be scored using the ECOG PS scale index (Appendix 6).

8.3.6 Clinical Laboratory Assessments

Selected prebaseline laboratory data (ie, LDH, albumin, neutrophils, lymphocytes, platelets, and hemoglobin since failure of last prior therapy), sampled on date(s) concomitant with prior CT scan(s) (alternatively most adjacent date), will be collected to explore correlations with tumor growth kinetics, if available.

Blood samples for serum chemistry, hematology, and other laboratory tests will be collected as indicated in the Schedule of Activities (see Section 1.3) and further described in Appendix 2, including Table 10-1. The investigator must review the laboratory results, document this review, and record any clinically relevant changes occurring during the trial.

Clinically significant abnormal laboratory findings are those which are not associated with the underlying disease, unless judged by the investigator to be more severe than expected for the subject's condition.

Local laboratory test results should be assessed for abnormalities. Laboratory abnormalities that are considered clinically significant, induce clinical signs or symptoms, require concomitant therapy, or require changes in trial treatment should be documented as an AE (see Appendix 3 for additional information on reporting of laboratory abnormalities that are considered AEs). When an abnormal laboratory or test result corresponds to a sign/symptom of an already reported AE, it is not necessary to separately record the laboratory/test result as an additional event. *Note: A CTCAE grade 3 or 4 laboratory result abnormality does not automatically indicate an SAE*.

8.4 Adverse Events and Serious Adverse Events

Timely, accurate, and complete reporting and analysis of safety information from clinical studies are crucial for the protection of subjects, investigators, and the sponsor, and are mandated by regulatory agencies worldwide. The sponsor has established SOPs in conformity with regulatory requirements worldwide to ensure appropriate reporting of safety information; all clinical studies conducted by the sponsor or its affiliates will be conducted in accordance with those procedures. Information in this section should be used in conjunction with the additional details provided in Appendix 3.

8.4.1 Definition of Adverse Events and Serious Adverse Events

The definitions of AEs, SAEs, AESIs as well as attribution definitions; severity criteria; special reporting situations; and procedures are provided in Appendix 3.

8.4.1.1 Adverse Events of Special Interest

For GEN1053, the following events have been defined as AESIs, irrespective of relatedness to trial treatment:

- AEs of thrombocytopenia (ie, low PLT counts that are considered clinically significant, induce clinical signs or symptoms, require concomitant therapy, or require changes in trial treatment)
- AEs of bleedings

AESIs can be serious or nonserious, as per standard seriousness criteria (Appendix 3). For AESIs requiring expedited reporting, please see Section 8.4.3.5. AESIs defined for treatment with IM will be determined and amended before starting phase 1b.

8.4.1.2 Other Events of Interest

Infusion-Related Reactions

IRRs are defined as any AE occurring during infusion or where the onset of the event occurs within 24 hours after ended infusion. For IRRs, the causality of the event should be judged as "related" by the investigator.

Investigators should consider the clinical picture and isolated events, such as "fatigue," occurring within 24 hours after the end of infusion and assess whether they do or do not constitute an IRR (refer to Section 6.7.2.3 for further IRR treatment guidance).

8.4.2 Adverse Event Reporting

As noted in Section 8.1.3, medical conditions (signs, symptoms, and diagnosis) that occur after the ICF is signed and prior to the first dose should only be reported as AEs if they were assessed by the investigator to be caused by a protocol-mandated procedure (ie, tumor biopsy and/or CT scan), including wash-out or discontinuation of prior medications.

All other AEs, whether serious or nonserious (see definitions in Appendix 3), will be documented from the first dose of trial treatment until the last safety follow-up visit, subject withdrew consent, subject started new anticancer treatment, or the subject dies, whichever comes first. The safety reporting periods are defined in Table 8-1.

Trial Period	Reporting Requirements		
Signing of ICF until first dose of trial treatment	AEs, if assessed by the investigator to be caused by a protocol-mandated procedure (eg, tumor biopsy, CT scan), including wash-out or discontinuation of prior medications.		
First dose of trial treatment through SFU2	All AEs and SAEs (see definitions in Appendix 3), regardless of causality, will be documented.		
After SFU2 through end of trial/after end of trial	There is no requirement to monitor subjects for AEs and SAEs following the protocol-required safety reporting periods or after end of trial. However, if the investigator becomes aware of an SAE, it must be reported if judged by the investigator as related to trial treatment.		
Refer to Appendix 3 for additional guidance for recording and reporting AEs and Section 7.1.1 for timing of			

Table 8-1 Reporting Period and Requirements

Refer to Appendix 3 for additional guidance for recording and reporting AEs and Section 7.1.1 for timing of safety follow-up visit(s).

NOTE: Any second primary malignancy(ies) regardless of relatedness to trial treatment, should be reported as an SAE at any time during or after the trial if the investigator becomes aware of such an event (see Section 8.4.3.1). AE=adverse event; CT=computed tomography; ICF=informed consent form; SAE=serious adverse event SFU2=safety follow-up visit 2.

For details regarding follow-up of AEs and SAEs and reporting period for SAEs judged as related to GEN1053 and/or IM, see Section 8.4.6. Refer to Section 6.2 for guidance regarding product complaints.

8.4.3 Events Requiring Immediate Reporting

Refer to Appendix 3 for additional guidance for recording and reporting AEs.

8.4.3.1 Second Primary Malignancy

Secondary primary malignancy(ies) (not a metastasis of the cancer under trial), regardless of relatedness to trial treatment, must be reported to the sponsor as SAEs within 24 hours of knowledge of the event (at any time during or after the trial).

8.4.3.2 Serious Adverse Events

All SAEs occurring during the safety reporting period must be reported from the trial site to the sponsor no later than 24 hours following:

- The subject visit at which the SAE was reported, noted, or recognized
- The principal investigator's or any investigator personnel's receipt of the test results
- Other information from which the SAE was reported, noted, or recognized

8.4.3.3 Overdose/Medication Errors

Overdoses are defined in Section 6.8. All cases of overdose with trial treatment, whether associated with an AE or not, must be reported to the sponsor within 24 hours of knowledge of the event. Overdose of concomitant medication should only be reported if associated with AEs whether serious or not.

Medication errors (including infusion rate errors) and uses outside what is foreseen in the protocol, including misuse and abuse of trial treatment, whether associated with an AE or not, should be reported to the sponsor within 24 hours of knowledge of the event. Medication errors related to concomitant medication should only be reported if associated with AEs whether serious or not.

8.4.3.4 Pregnancy

Pregnancy is not allowed in this trial. However, if any pregnancy occurs during trial participation, the pregnancy must be reported using the pregnancy reporting paper form available in the investigator site file.

All reports of pregnancy in female subjects or partners of male subjects must be reported to the sponsor within 24 hours of knowledge of the event, using the pregnancy reporting paper form available in the investigator site file. In the case of pregnancy in the partner of a male subject, a separate ICF will be obtained from the female partner for collection of information regarding the pregnancy.

The pregnancy must be followed up to determine outcome (including premature termination) and status of mother and child. The child must be followed at least to the age of 1 month. Pregnancy complications and elective terminations must be reported as an AE or SAE. Spontaneous abortions must be reported as an SAE. Any SAE occurring in association with a pregnancy brought to the investigator's attention after the subject has completed the trial and considered by the investigator as possibly related to the IMPs and AMPs must be promptly reported to the sponsor or designee.

Pregnant trial subjects must be withdrawn from treatment immediately, whereas male subjects may continue in the trial should pregnancy of female partners occur.

8.4.3.5 Adverse Events of Special Interest or Other Events of Interest

AESIs in this protocol are defined in Section 8.4.1.1.

The following AESIs need to be reported to the sponsor within 24 hours of awareness irrespective of event seriousness:

- Grade 3+ thrombocytopenia (ie, AEs of thrombocytopenia with PLT count less than 50×10⁹/L)
- Grade 2+ bleedings (ie, bleeding that requires medical intervention/hematocrit monitoring, as per CTCAE criteria per type of bleeding)
 Note: AEs of grade 1 bleedings and of ≤ grade 2 thrombocytopenia must be reported as per regular AE timelines, depending on whether they fulfill or not any seriousness criterion based on the investigator's assessment.

All AESIs will be closely monitored to timely identify, quantify and qualify any relevance of the nonclinical findings to humans and the adequacy of the mitigation strategies described in Sections 2.3.2, 2.2.2.1, 2.2.3.1 and 6.7.2. All AESIs will be taken into consideration during DEC reviews and SC decisions, regardless of their occurrence (within or outside the DLT period).

8.4.4 Regulatory Reporting Requirements for SUSARs

The sponsor has a legal responsibility to notify, as appropriate and according to local regulations, both the local regulatory authority and other regulatory agencies about the safety of the product(s) under clinical investigation. Prompt notification of SAEs by the investigator to the sponsor is essential so that legal obligations and ethical responsibilities towards the safety of subjects are met (see Section 8.4.3.2).

The sponsor will ensure that all relevant information about SUSARs is documented and reported as soon as possible, but within a maximum of 15 calendar days (fatal or life-threatening SUSARs within a maximum of 7 calendar days) of first knowledge by the sponsor or designee, to the competent regulatory authorities and/or to the ethics committee/IRBs according to the applicable local regulatory requirements. Relevant follow–up information of fatal or life-threatening SUSARs will be communicated subsequently within the required reporting timelines. The sponsor will also communicate relevant information on SUSARs with the investigators in predefined periods and according to local regulations.

The investigator should be aware of local reporting regulations to the IEC/IRB. The CRO will either supply the investigator with the reports which should be passed on to the IEC/IRB or report directly to the IEC/IRB, depending on local regulations. SUSARs aggregated line listings will be distributed quarterly, or every 6 months, or in periods as warranted for regulatory compliance; the investigator must review such safety information in a timely manner and signoff for the review as instructed by the sponsor, to document the awareness about the latest safety updates that may impact on the investigator's responsibilities for subject care.

8.4.4.1 Regulatory Reporting Requirements for AMPs

Where an AE is suspected to be related only to an AMP, and does not result from a possible interaction with the IMP, safety reporting will be done by the sponsor in accordance with Chapter 3 of TITLE IX of Directive 2001/83/EC.

8.4.5 Disease-Related Events/Outcomes and Other Events/Procedures Not Qualifying as Adverse Events or Serious Adverse Events

The following should not be reported as an AE or SAE:

- Events that are clearly consistent with the expected pattern of the underlying disease or its progression should not be recorded as AEs or SAEs.
 - That is, the terms "Disease Progression"; "Progression of Disease"; or "Malignant Disease Progression" and other similar terms should not be used to describe an AE or SAE. These data are captured as efficacy assessment data only.
 - In most cases, the expected pattern of progression will be based on the response criteria. In rare cases, the determination of clinical progression will be based on symptomatic deterioration. However, every effort should be made to document progression through use of objective criteria.

- Clinical symptoms may be reported as AEs or SAEs if the symptom cannot be determined as reasonably due to progression of the underlying malignancy or does not fit the expected pattern of progression for the disease under study.
- Hospitalization due solely to progression of the underlying cancer should not be reported as an SAE. See Appendix 3, under the definition of SAE, for additional reasons when hospitalizations should not be reported as SAEs.

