2.2.2.1 Summary of Nonclinical Studies - Monotherapy

A nonclinical data package, consisting of nonclinical pharmacology and toxicology studies in vitro, in vivo, and ex vivo, is available for GEN1053:

- GEN1053 binds human CD27 with an affinity in the nanomolar range and showed dosedependent binding to CD27⁺ human CD4⁺ and CD8⁺ T cells.
- In vitro, GEN1053 increased proliferation of human healthy donor T cells that had been activated through TCR crosslinking with EC₅₀ values in the subnanomolar range. GEN1053 showed increased potency compared to benchmark IgG1 CD27 antibodies. CD27 agonist activity of GEN1053 was independent of the presence of FcγR-mediated crosslinking in contrast to benchmark antibodies.
- GEN1053 increased T-cell proliferation, activation, and cytokine production in the presence of an enhanced PD-1/PD-L1 signaling axis.
- GEN1053 did not induce T-cell proliferation in the absence of TCR crosslinking.
- Ex vivo, GEN1053 increased the number of tumor-infiltrating lymphocytes in primary NSCLC tumor cultures. Moreover, vaccination studies in hCD27 transgenic mice demonstrated that GEN1053 was able to enhance the T-cell-mediated immune response in vivo.
- GEN1053 increased expression of T-cell activation markers (4-1BB, CD107a, CD69, CD25) and the production of IFN-γ, IL-1β, IL-6, IL-13, GM-CSF, and TNF-α in activated T cells in vitro.
- GEN1053 increased expression of the cytotoxicity-associated molecules GzmB and CD107a on T cells after exposure to tumor cells expressing their cognate antigen, with EC₅₀ values in the low nanomolar range. Moreover, GEN1053 increased antigen-specific tumor-cell kill in vitro.

The nonclinical pharmacology results support the premise that GEN1053 has the potential to increase antitumor effects in solid tumor indications that benefit from (re)activation of antitumor T-cell immunity.

Nonclinical Safety Studies:

Two repeat-dose IV toxicology studies (DRF and pivotal GLP) were conducted in cynomolgus monkeys with GEN1053 using dose levels of 0 (vehicle), 0.2 (DRF only), 1, 5, and 30 mg/kg (IV, 30 min infusion; DRF: 4 doses QW; GLP: 3 doses Q3W).

• The main adverse effect in the monkeys was severe thrombocytopenia, which became apparent from 10 to 12 days after the first dose and was followed by severe anemia, prolonged coagulation time, widespread bleeding with hemorrhagic diathesis, and led to

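### Section 8.4.5 makes no exception for AESIs, so a bleed attributed to the tumor can go unrecorded although the AESI definition disregards relatedness to treatment

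*Combined protocol and SAP*

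**What the plan says.** Section 8.4.5 lists what sites are not to report as an AE or SAE. Its first item reads: "Events that are clearly consistent with the expected pattern of the underlying disease or its progression should not be recorded as AEs or SAEs". The sub-item that explains it says that progression terms "and other similar terms should not be used to describe an AE or SAE". The next sub-item says that the expected pattern of progression will mostly follow the response criteria. A further item deals with symptoms: "Clinical symptoms may be reported as AEs or SAEs if the symptom cannot be determined as reasonably due to progression of the underlying malignancy", or if the symptom does not fit the expected pattern. AESIs are not mentioned.

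Section 8.4.1.1 says: "For GEN1053, the following events have been defined as AESIs, irrespective of relatedness to trial treatment". The two entries are AEs of thrombocytopenia and AEs of bleeding.

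The general rules on collection are broad. Table 8-1 in Section 8.4.2 says, for the period from first dose to the second safety follow-up visit: "All AEs and SAEs (see definitions in Appendix 3), regardless of causality, will be documented". Appendix 3 also asks for all AEs whether or not treatment-related, but refers to Section 8.4.5 for the disease-related events that do not qualify as AEs.

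Section 8.4.3.5 requires grade 2 or higher bleeding AESIs to reach the sponsor within 24 hours and says: "All AESIs will be taken into consideration during DEC reviews and SC decisions, regardless of their occurrence". Section 6.7.2.3 separately requires a 24-hour report of grade 2 or higher bleeding events. Section 9.4.3.1 tabulates on-treatment AESIs.

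**The concern.** Bleeding is a risk that this trial is set up to watch. The monkey studies showed severe thrombocytopenia followed by "prolonged coagulation time, widespread bleeding with hemorrhagic diathesis", the mechanism is uncertain, and Section 2.3.3 names bleeding episodes among the events to be closely monitored. Section 8.4.3.5 says the AESIs serve to judge whether those findings carry over to humans. AEs are also a primary endpoint (Table 3-1).

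The AESI definition sets aside relatedness to treatment so that the count does not depend on individual judgment. Section 8.4.5 asks for a related judgment at an earlier point: whether the event clearly fits the disease. If the answer is yes, the event is not an AE and the AESI definition is never reached.

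The current cohorts have no control arm. A drug effect that aggravates tumor bleeding would be hard to tell from disease bleeding in a single subject, and would show mainly as a high total rate. A rule that can remove some of those bleeds before recording can only lower that total.

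**Working it through.** The plan states no figure on this point, so the check is a reading of the sections in the order in which a site would apply them.

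1. **Is the event an AE?** Appendix 3 leaves disease-related events to Section 8.4.5. That section excludes events that clearly fit the disease or its progression, with no AESI exception.
2. **Is the AE an AESI?** Section 8.4.1.1 applies only to AEs of bleeding and AEs of thrombocytopenia. It ignores relatedness to treatment, but it cannot bring back an event stopped at step 1.
3. **Does Table 8-1 bring it back?** No. It covers AEs and SAEs regardless of causality, and an event excluded at step 1 is neither.
4. **Does the symptom item bring it back?** Not for a bleed that the investigator attributes to the tumor. It is permissive, and it covers symptoms that are not reasonably due to progression or do not fit its pattern.

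For a bleed that the investigator attributes to the tumor:

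| Bleed | Against recording | For recording | Result |
|---|---|---|---|
| Grade 1, new | 8.4.5 | Nothing specific: 8.4.3.5 puts grade 1 bleeding AEs on regular timelines, which presupposes an AE | Can go unrecorded |
| Grade 2 or higher, new | 8.4.5 | 6.7.2.3 and 8.4.3.5: 24-hour report, no disease exception | Conflicting instructions |
| Worsening of a condition present before first dose | 8.4.5 | 8.1.3: worsening is documented as an AE | Conflicting instructions |

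Section 8.4.3.5 introduces its 24-hour list as a list of AESIs, so it too presupposes an AE. Section 6.7.2.3 speaks of bleeding events and is the stronger counter-instruction.

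**Size.** The documents give no rate of tumor bleeding for HNSCC, NSCLC or the escalation tumor types, and no share that investigators would attribute to disease. The following is an illustration on assumed inputs only. Suppose 8 of 40 subjects in an expansion cohort bleed (8/40 = 20%; exact 95% CI 9.1–35.6%) and a share s goes unrecorded. The recorded count is 8 × (1 − s):

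- s = 25%: 6/40 = 15% (5.7–29.8%)
- s = 50%: 4/40 = 10% (2.8–23.7%)
- s = 75%: 2/40 = 5% (0.6–16.9%)

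Only the most extreme of these shares gives an interval that excludes the assumed 20%. With s = 0 there is no loss.

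**The case against.** The strongest reply is that the sections work in sequence and do not contradict each other: 8.4.5 settles what is an AE, and 8.4.1.1 settles which AEs are AESIs. On this view 8.4.5 is housekeeping. Its own explanation concerns progression terms, its expected pattern is tied to the response criteria, and bleeding is not a RECIST criterion. It reaches only events that clearly fit the disease, so doubt favors reporting, and drug-aggravated bleeding of uncertain cause is hard to call clear. Sections 6.7.2.3 and 8.4.3.5 demand 24-hour reports of grade 2 or higher bleeding, and Section 6.7.2.3 tells subjects with even mild bleeding to contact the site at once. Section 8.1.3 makes worsening of an existing condition an AE. Exclusion criterion 1m keeps out subjects with a known history or high risk of bleeding requiring transfusions or hospitalizations, unless the sponsor approves.

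Much of this stands, and it limits the point. A reader might infer that every bleed is an AESI and that tumor bleeding is simply lost, with no 24-hour report. The documents do not support that: 8.4.1.1 is confined to AEs, the exclusion is confined to clear cases, and the 24-hour rules carry no disease exception. Nor do the documents say that bleeding belongs to the expected pattern of HNSCC or NSCLC; that some investigators would judge it so is an assumption.

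The reply does not close the gap. The parent sentence in 8.4.5 speaks of events and of the disease as well as its progression, and the symptom item shows that the section reaches beyond terminology. Reading the sections in sequence is what places attribution ahead of recording. Nothing in 8.4.5 says that the bleeding rules override it.

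**Conclusion.** The gap is real but narrower than a direct contradiction. A bleed attributed to the tumor can go unrecorded as an AE and so miss the AESI tables and the AESI reviews by the dose escalation and safety committees. This applies to any tumor type, in escalation as well as expansion. The exposure is clearest for new grade 1 bleeding. For grade 2 or higher, the fault is that sites hold conflicting instructions; it is not established that reports would be lost.

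The direction of any error is downward, because the rule can only remove events. Its size cannot be derived from the documents. A reader might take the illustrative counts as an estimate of bias, or as showing that the reported interval would miss the true rate. They show neither: both the bleed rate and the unrecorded shares are assumed. The conclusion rests on the wording and on one assumption, that some investigators would judge some bleeds clearly consistent with the tumor. It merits correction at the next amendment because the count feeds safety decisions and the change is cheap.

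**What to change.** Add to Section 8.4.5 that the exclusion does not apply to the AESIs in Section 8.4.1.1 (bleeding and thrombocytopenia), and that these are always recorded as AEs whatever their attribution. Capture suspected tumor-site or disease origin in a separate eCRF field. The existing item cannot serve, because Appendix 3 asks only whether an event is related to trial treatment, and an unrelated event need not come from the tumor. Cross-refer to the exemption from Sections 8.4.1.1 and 8.4.3.5. Keep the bar on disease progression as an AE term.

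The exemption should stop at the AESIs. Extending it to the event types in Section 6.7.1 would bring in all grade 5 events, so that deaths from progression would have to be recorded as AEs, against the bar that is being kept.

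The cost is a short text change, one eCRF item and a few more AE forms. The tabulated bleeding rate will be higher and will include disease-related bleeds, which the new field allows to be shown separately. No dosing or management rule changes.
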